3.2. Study Day and Treatment Day

For efficacy endpoints analyses, study day is defined as the number of days from randomization date to the event/visit date. It is calculated as follows:

- If the event date falls on or after randomization date,

Study day = Event or visit date – randomization date + 1

- If the event date falls before randomization date,

Study day = Event or visit date – randomization date

For safety endpoints analyses, treatment day is defined as the number of days from DB first dose date to the event/visit date. It is calculated as follows:

- If the event date falls on or after DB first dose date,
Treatment day = Event or visit date –DB first dose date + 1
- If the event date falls before DB first dose date,
Treatment day = Event or visit date –DB first dose date

3.3. Analysis Visits and Study Period

For efficacy analyses, DB period is defined from randomization up to the first OLE dose if subjects enter OLE treatment period, or end of study in subjects not enrolled in OLE period, unless specified. OLE period is defined from OLE first dose up to the end of study. If assessment time is available, assessments should be further differentiated by time compared to OLE first dose. If assessments are collected on the same day as OLE first dose date and no assessment times are available, those assessments should be counted into DB period.

For safety analyses, DB period is defined from first dose up to the first OLE dose if subjects enter OLE treatment period, or end of study if subjects not enrolled in OLE period.

Efficacy assessments

For the efficacy assessment, the reference date for the derivation of relative days of events or findings will be the randomization day. If a subject receives treatment dose prior to the randomization by mistake, the reference date of efficacy assessment will be the date of the first treatment dose administration for that subject.

For the daily WI-NRS, weekly average will be aligned by study periods. For DB period, weekly average will be calculated based on every 7 days increment starting on Day 1. For week 16, only assessments before the first dose of OLE period will be included for weekly average calculation. Time windows are specified in [Table 2](#) below.

Table 2: Time window of weekly average WI-NRS in DB period

Analysis week	Time windows referring to randomization date
Baseline	-7 to -1
Week 1	1 - 7
Week 2	8 - 14
Week 3	15 - 21
Week 4	22 - 28
Week 5	29 - 35
Week 6	36 - 42
Week 7	43 - 49
Week 8	50 - 56

Week 9	57 - 63
Week 10	64 - 70
Week 11	71 - 77
Week 12	78 - 84
Week 13	85 - 91
Week 14	92 - 98
Week 15	99 - 105
Week 16	106 - min(113, Day of OLE first dose)

The time window of weekly average NRS in OLE period will start from the day after the first dose of OLE period as specified in [Table 3](#).

Table 3: Time window of weekly average WI-NRS in OLE period

Analysis week	Time windows referring to OLE first dose date
Week 17 - OLE	2 - 8
Week 18 - OLE	9 - 15
Week 19 - OLE	16 - 22
Week 20 - OLE	23 - 29
Week 21 - OLE	29 - 36
Week 22 - OLE	37 - 43
Week 23 - OLE	44 - 50
Week 24 - OLE	51 - 57
Week 25 - OLE	58 - 64
Week 26 - OLE	65 - 71
Week 27 - OLE	72 - 78
Week 28 - OLE	79 - 85
Week 29 - OLE	86 - 92
Week 30 - OLE	93 - 99
Week 31 - OLE	100 - 106
Week 32 - OLE	107 - 113
Week 33 - OLE	114 - 120
Week 34 - OLE	121 - 127
Week 35 - OLE	128 - 134
Week 36 - OLE	135 - 141

Week 37 - OLE	142 - 148
Week 38 - OLE	149 - 155
Week 39 - OLE	156 - 162
Week 40 - OLE	163 - 169
Week 41 - OLE	170 - 176
Week 42 - OLE	177 - 183
Week 43 - OLE	184 - 190
Week 44 - OLE	191 - 197
Week 45 - OLE	198 - 204
Week 46 - OLE	205 - 211
Week 47 - OLE	212 - 218
Week 48 - OLE	219 - 225
Week 49 - OLE	226 - 232
Week 50 - OLE	233 - 239
Week 51 - OLE	240 - 246
Week 52 - OLE	247 - EOS

For other efficacy variables, all available values of scheduled measurements will be assigned to the appropriate visit window according to [Table 4](#). In the event of multiple measurements of the same test in the same window, the one closest to the targeted visit date will be used for the by-visit summary. If they are at the same number of days away from the target day, the latest one will be used.

Table 4: Time window for other efficacy variables in DB period

Visit	Target day referring to randomization	Time windows			
		Sleep Loss VAS, GA-CNPG-S, IGA-CNPG-A, PN-NAT, PN-IGA, PGI-PN-S	ItchyQoL	PHQ-9, GAD-7	PGIC
Baseline*	1	≤1	≤1	≤1	
Week 2	15	2 - 22			
Week 4	29	23 - 43	2- 43		2- 43
Week 8	57	44 - 71	44 - 71	2 - 85	44 - 71
Week 12	85	72 - 99	72 - 99		72 - 99
Week 16	113	100 - OLE first dose	100 - OLE first dose	86 - OLE first dose	100 - OLE first dose

The visit mapping in OLE period will start from the day after the first dose of OLE period based on the time window specified [Table 5](#).

Table 5: Time window for other efficacy variables in OLE period

Visit	OLE first dose date	Time windows
		Sleep Loss VAS, GA-CNPG-S, IGA-CNPG-A, PN-NAT, PN-IGA, PGI-PN-S, ItchyQoL, PHQ-9, GAD-7, PGIC
Week 18 - OLE	15	2 - 22
Week 20 - OLE	29	23 - 71
Week 32 - OLE	113	72 - 169
Week 48 - OLE	225	170 - 239
Week 52 - OLE	253	240 - EOS

Safety assessments

For the safety assessment, the reference date for the derivation of relative days of events or findings will be the DB first dose date. Selected safety variables will be summarized by the analysis window defined in [Table 6](#) for the by visit descriptive analysis. In the event of multiple measurements of the same test in the same window, the one closest to the targeted visit date will be used for the by-visit summary. If they are at the same number of days away from the target day, the latest one will be used.

Table 6: Time window for safety endpoints in DB period

Visit	DB first dose	Time windows		
		Physical examination, Vital signs, Body weight, Clinical lab blood tests	ECG Pregnancy test	Urinalysis
Baseline*	1	ADA	≤ 1	≤ 1
Week 2	15		2 - 22	
Week 4	29		23 - 43	

Week 8	57	44 - 71	2 - 85
Week 12	85	72 - 99	
Week 16	113	100 - OLE first dose	86 - OLE first dose 2 - OLE first dose

* up to first dose date/time

The visit mapping in OLE period will start from the day after the first dose of OLE period using the time window specified in [Table 7](#).

Table 7: Time window for safety variables in OLE period

Visit	date	Time windows		
		Physical examination, Vital signs, Body weight, Clinical lab blood tests	ECG	Urinalysis, Pregnancy test
Target Day referring to OLE first dose	ADA			
Week 18 - OLE	15	2 - 22		
Week 20 - OLE	29	23 - 71		
Week 32 - OLE	113	72 - 169		2 - 169
Week 48 - OLE	225	170 - 239		170 - 239
Week 52 - OLE	253	240 - EOS	2 - EOS	240 - EOS

3.4. Missing Data Handling

No imputations will be performed for missing data for safety endpoints, unless otherwise specified. Missing data handling for efficacy endpoints are specified in [Section 4.6](#).

3.5. Timing of Analyses

The primary efficacy analyses may be conducted after the last subject has completed the DB period. The final analyses including OLE data will be conducted after last subject has completed the last OLE visit and study.

4. STATISTICAL METHODOLOGY AND ANALYSES

4.1. Subject Disposition

The subject disposition will be summarized by treatment and overall, and by study periods. All information will be presented in numbers and percentages in a summary table. The following information will be presented in the subject disposition table:

- Randomized subjects

- Safety analysis set
- mITT analysis set
- OLE analysis set
- Subjects who completed DB treatment
- Subjects discontinued DB treatment and the primary reasons for DB treatment discontinuation
- Subjects who completed DB period
- Subjects discontinued DB period and the primary reasons for DB period discontinuation
- Subjects who completed OLE treatment
- Subjects discontinued OLE treatment and the primary reasons for OLE treatment discontinuation
- Subjects who completed OLE
- Subjects discontinued OLE and the primary reasons for OLE discontinuation
- Duration of DB period in weeks: (DB period end date – randomization date +1)/7
- Duration of OLE period in weeks: (OLE period end date – DB period end date)/7
- Time on study in weeks: [max (DB period end date, OLE period end date) – randomization date+1]/7

4.2. Demographics and Baseline Characteristics

The demographics and baseline characteristics data will be summarized for the mITT and safety analysis sets. Descriptive statistics will be provided for continual variables. Numbers and percentages of subjects will be tabulated for categorical variables.

4.2.1. Demographics

The following demographic variables will be summarized:

Age (years), calculated as the number of years between the date of birth and the date of signing the Informed Consent form.

- Age (years)
- Sex (Male or Female), Childbearing potential status for female.
- Race (White, Black or African American, Asian, American Indian or Alaska Native, Native Hawaiian or Other Pacific Islander, Other)
- Ethnicity (Hispanic or Latino, Not Hispanic or Latino)
- Height (cm)
- Weight (kg)

- $BMI \text{ (kg/m}^2\text{)} = \text{Weight(kg)}/\text{Height(m)}^2$

4.2.2. Baseline and Disease Characteristics

The following baseline characteristics will be summarized.

- Years since first PN nodules (calculated relative to first dose date)
- Years since diagnosis (calculated relative to first dose date)
- Elevated IgE: High ($>200 \text{ IU/mL}$), normal ($\leq 200 \text{ IU/mL}$)
- Co-morbidities includes, but not limited to, history of atopy, anxiety or depression, allergy, dermatologic conditions, lipid disorders, hypertension, type 2 diabetes, and chronic renal disease.
- Smoking status
- Treated with KPL-716 in previous KPL-716 studies (yes, no)

4.2.3. Medical History

The medical history is coded using Medical Dictionary for Regulatory Activities (MedDRA) of the version at database lock. The summary of medical history will be presented with number (%) by System Organ Class (SOC) and Preferred Term (PT). Each subject will be counted only once for each PT within a SOC per cohort. Similarly, for determination of MedDRA SOC incidences, subjects who experience multiple medical conditions under the same SOC will be counted only once for that SOC.

4.3. Prior and Concomitant Medications and procedures

4.3.1. Prior and Concomitant Medications

All medications will be coded using the World Health Organization (WHO) Drug Dictionary of the version at database lock.

Prior medications are defined as medications that started before the first dose of study drug. Concomitant medications are defined as medications that (1) started before the first dose of study drug and continued into the treatment period, or (2) started on or after the date of the first dose of study drug. The number (%) of subjects who took prior and concomitant medications will be summarized on the anatomical class (ATC level 3) and PT by treatment and overall subjects. For subjects who enter OLE, concomitant medications which start on or before OLE 1st dose will be summarized into DB period, otherwise into OLE.

Prior Topical corticosteroid (TCS) regardless of indication, systemic corticosteroid, intralesional corticosteroid, and oral antihistamine will be summarized as well, of which identification will be based on medical review.

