7. Sexually active male subjects must have documented vasectomy or must agree to use a highly effective method of contraception as defined above with their partners of childbearing potential from first dose until 16 weeks after final study drug administration.
8. Male subjects must agree to refrain from donating sperm from first dose until 16 weeks after the last study drug administration. Female subjects must agree to refrain from donating eggs from first dose until 16 weeks after the last study drug administration.
9. Female of childbearing potential must have a negative serum  $\beta$ -human chorionic gonadotropin ( $\beta$ -hCG) test at the Screening Visit and negative urine pregnancy test on Day 1.
10. Able to comprehend and willing to sign an Informed Consent Form and able to abide by the study restrictions and comply with all study procedures for the duration of the study.
11. Subjects must be on optimized and stable treatment for co-morbidities for at least 28 days prior to Day 1.

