#### **8.7.5 Concomitant Medications**

Concomitant medications will be coded using WHO Drug Dictionary and will be classified by Anatomical Therapeutic Chemical (ATC) classification level 4 and PT for the Safety Analysis Set. Frequencies and percentages of subjects using each concomitant medication will be presented for the Safety Analysis Set overall, and by treatment group. All medication use will be listed regardless of the timing of the start of the medication.

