1.2. Study Design

This is a randomized, double-blind, placebo-controlled study to investigate the efficacy, safety, tolerability, PK, and immunogenicity of KPL-716 administered SC in subjects with moderate to severe PN experiencing severe pruritus.

[figure not shown]
The Phase 2b study ([Figure 1](#)) consists of a 4-week screening period and a 16-week double-blind (DB) period, followed by a 36-week open-label-extension (OLE) period. Approximately 180

subjects with moderate to severe PN experiencing severe pruritus will be randomized (at 1:1:1:1 ratio) into one of the following 4 arms:

- Arm A: KPL-716, 540 mg, SC, every 4 weeks (Q4W)
- Arm B: KPL-716, 360 mg, SC, Q4W
- Arm C: KPL-716, 120 mg, SC, Q4W
- Arm D: Placebo, SC, Q4W

A total of 4 doses of study drug will be administered during the DB Period to measure the efficacy, safety, and PK of KPL-716.

Figure 1 Phase 2b Study Design Diagram

After the DB period, all subjects will have the option to receive KPL-716 360 mg SC, Q2W during the OLE period to evaluate the long-term safety and PK of KPL-716. For subjects who complete the DB period but choose not to participate in OLE, or who terminate earlier, an End of Study (EOS) visit will be required 4 weeks following the date of last study drug dose.

Subjects will follow the schedule below:

- Screening period (minimum 7 days and maximum 28 days)
- DB period (Day 1 [Baseline] to Week 16)
- OLE period (End of Week 16 to Week 52)

The allowable visit window from Week 2 to Week 16 is \pm 2 days and thereafter to Week 52 is \pm 3 days.

Randomization and Dosing:

Subjects will be randomized 1:1:1:1 into one of the following 4 arms: KPL-716 540 mg SC, Q4W; KPL-716 360 mg SC, Q4W; KPL-716 120 mg SC, Q4W; or placebo SC, Q4W. At the end of DB period, all subjects will have the option to enter the OLE period to receive KPL-716

360 mg SC Q2W. Stratification will be performed based on sex and years since first nodule observed (i.e., ≥ 10 years vs. < 10 years).

Efficacy Assessments:

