4.6.6. Rescue medications and prohibited medications

Rescue medications are allowed under specific guidance as specified in Pharmacy Manual Version 3.0, Dated 06 October 2021 ([Table 9](#)).

Table 9: Rescue medications listed in pharmacy manual

Tier 1	Antihistamines, oral: 
 • Diphenhydramine • Cetirizine
Tier 2	
 • Hydrocortisone ointments, up to 2.5% • Desonide cream, lotion 0.05%
Tier 3	Non-Europe countries 
 • Triamcinolone acetonide, 0.1% • Fluocinolone Acetonide, 0.025% Europe countries 
 • Fluticasone propionate cream/ointment, up to 0.05%
Tier 4	Clobetasol propionate, 0.05%

For analysis purpose, TCS, oral/IV antihistamines, topical antihistamine, corticosteroid intralesional injection, and/or systemic corticosteroids, which were used to reduce pruritus or treat PN skin lesion on and after first dose date and have significant impact on efficacy interpretation, are defined as rescue medications. TCS which are deemed to have minimum impact on efficacy interpretation are not considered as rescue medications. For example, TCS used for injection site reactions which are not overlapping with the subject's PN lesions are not considered as rescue medication. Antihistamines targeting H2 receptor are not considered as rescue medications due to no impact on pruritis. Identification of rescue medications will be based on medical review in a blinded way before database lock.

Additionally, the protocol specified a list of medications which are prohibited from designated timepoints before Day 1 and throughout the study. Prohibited medication which impact on efficacy analyses will be identified based on blind medical review before database lock as well.

Number of subjects who used rescue/prohibited medications and days on rescue/prohibited medications will be summarized by study periods. Rescue/prohibited medications which overlap with both DB and OLE periods will be summarized based on proportion of days in each period. Use of rescue/prohibited medications over time will be summarized by weeks which will be defined consistently as weeks of WI-NRS. Time to 1st use of rescue/prohibited medications will be summarized based entire study period.

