4.7.1. Adverse Events

Adverse events will be mapped to PT and SOC using the most up to date MedDRA of the version at database lock. A treatment-emergent AE (TEAE) is defined as any event not present before exposure to study drug or any event already present that worsens in either intensity or frequency after exposure to study drug. Furthermore, if an AE cannot be determined as treatment-emergent due to incomplete/missing date, conservatively, it will be considered as treatment emergent and included in the summary tables. For subjects who enter OLE, TEAEs which occur (based on AE start dates) before OLE first dose date will be summarized into DB period, otherwise into OLE period. If AE occurring time is available, time should be compared to OLE first dose date and time for AE period derivation.

The following TEAE summaries will be summarized as an overview.

- Any TEAEs
- Drug-related TEAEs
- TEAE by maximum severity (mild, moderate, severe)
- Serious TEAEs (SAEs)
- Drug related serious TEAEs
- TEAEs leading to dose interruption
- TEAEs leading to treatment discontinuation
- TEAEs leading to study discontinuation
- Death
- TEAE of special interest

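### SAP 4.3.1 places each concomitant medication in the double-blind or OLE period by start date alone, so drugs still being taken at OLE entry are omitted from the OLE summary

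*SAP*

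**What the plan says.** SAP 4.3.1 first defines what counts as concomitant. One limb covers a drug that "started before the first dose of study drug and continued into the treatment period"; the other covers a drug started on or after the first dose. The section then plans a count and percentage of subjects who took each medication, and sets the period rule for subjects who enter the OLE: "concomitant medications which start on or before OLE 1st dose will be summarized into DB period, otherwise into OLE". Stop date and ongoing status play no part in that rule.

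SAP 4.6.6 treats a subset of these drugs differently: "Rescue/prohibited medications which overlap with both DB and OLE periods will be summarized based on proportion of days in each period".

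For treatment-emergent adverse events (TEAEs), SAP 4.7.1 says: "TEAEs which occur (based on AE start dates) before OLE first dose date will be summarized into DB period, otherwise into OLE period". It adds that clock times are compared where they are available.

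On background treatment, Protocol 4.7.1 (criterion 11) says: "Subjects must be on optimized and stable treatment for co-morbidities for at least 28 days prior to Day 1".

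Protocol 8.7.5 plans the table without a period split: "Frequencies and percentages of subjects using each concomitant medication will be presented for the Safety Analysis Set overall, and by treatment group". It also lists all medication use, whenever it began. SAP 4.3.2 defines prior and concomitant procedures along the same lines as medications.

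**The concern.** A table headed as OLE concomitant medication will be read as showing what subjects were taking during the OLE. Under the stated rule it shows only what they began after the first OLE dose. A subject on a long-term drug throughout the extension is not counted for it there unless a new record for that drug begins in the OLE.

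The OLE covers 36 of the 52 weeks and exists mainly for long-term safety and PK. Background medication is part of the context for reading its adverse events. SAP 4.2.2 expects co-morbidities such as hypertension, lipid disorders, type 2 diabetes and chronic renal disease, for which treatment is usually long-term. The drugs most relevant as background are therefore the ones most likely to be missing from the table.

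**Working it through.** The plan gives no figure to reproduce, so the check applies the rule to each type of record and compares the result with counting by overlap, the logic used in the SAP's definition of concomitant and in SAP 4.6.6.

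| Record, for a subject who enters the OLE | SAP 4.3.1 period rule | Counting by overlap |
|---|---|---|
| Started before Day 1, taken to Week 52 | DB only | DB and OLE |
| Started during DB, continued past the first OLE dose | DB only | DB and OLE |
| Started on the day of the first OLE dose (no time recorded), continued | DB only | OLE counted; DB depends on the same-day rule |
| Started after the first OLE dose | OLE only | OLE only |
| Started during DB and stopped before the first OLE dose | DB only | DB only |

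The rules differ in the first three rows. No other section of either document returns an ongoing ordinary medication to the OLE summary.

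**Illustration of the first row.** The study schedule gives 16 DB weeks and 52 − 16 = 36 OLE weeks. For a subject who completes Week 52, 16/52 = 31% of on-study use falls in DB and 36/52 = 69% in the OLE. The current rule places the record wholly in DB.

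**Which drugs are affected.** Criterion 11 requires stability for at least 28 days before Day 1. Treatment meeting it began well before the first OLE dose, which is at about Week 16. If it continues, it falls in the first row. Treatment newly started during the OLE is still counted.

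**Size.** Suppose, as an assumption only, that 40% of OLE subjects take a drug class throughout, all from before Week 16. Let f be the share of those users who also have a new record in that class after the first OLE dose. Their contribution to the OLE table is 40% × f:
- f = 0: 0% is shown, a shortfall of 40 percentage points.
- f = 1: 40% is shown, with no shortfall at class level.

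The documents give neither the prevalence nor f, so the true value within this range cannot be stated.

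**Overlap with SAP 4.6.6.** A rescue or prohibited drug is also a concomitant medication. If one record spans the first OLE dose, it is DB-only in the 4.3.1 table and divided between both periods in the 4.6.6 table.

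**Same-day rule.** With dates only, a drug started on the day of the first OLE dose goes to DB, while an adverse event of that date goes to the OLE. The event and the drug given for it can then sit in different periods.

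**The case against.** The strongest defence is that this is a deliberate single-count convention. Each record is shown once, in the period in which it began, just as a TEAE that starts in DB and continues into the OLE is shown only in DB. On that view the OLE table lists newly started medication, and a clearer title would be enough. The analogy does not carry over well. An adverse event is counted by its onset, whereas a medication is a continuing exposure, and the table reports subjects who took the drug. The SAP itself uses overlap when it decides whether a drug is concomitant at all.

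Other parts of the defence stand, and they rule out stronger conclusions that a reader might draw:
- *That 4.3.1 directly contradicts 4.6.6.* It does not. Section 4.6.6 governs a separate output in which days are counted. The two tables disagree only for rescue or prohibited records that span both periods; for ordinary drugs this is a difference in logic.
- *That adherence to monotherapy in the OLE cannot be judged.* The drugs that matter most for this are the rescue and prohibited ones. SAP 4.6.6 summarises those judged to affect efficacy by period and by week, and SAP 4.4 summarises important deviations by period.
- *That an ongoing drug class will print as 0% in the OLE.* That also requires that no user has a new in-class record during the OLE.
- *That data are lost.* Protocol 8.7.5 keeps all use in the listings.

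The same-day point is also small. It concerns one calendar day per subject, and the 4.3.1 wording refers to the dose rather than its date, so a recorded time could settle it.

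**Conclusion.** The point holds, as a minor one. As written, SAP 4.3.1 understates medication use in the OLE by leaving out treatments that were already under way at the first OLE dose and continued. That much long-term background medication is affected is an inference from criterion 11; it assumes that such treatment usually continues into the OLE. The documents support no figure for the amount.

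The consequence is limited to the descriptive OLE concomitant-medication summary and, because SAP 4.3.2 borrows the same definitions, probably the procedures summary. Double-blind efficacy and safety results do not change.

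**What to change.** Replace the period sentence in SAP 4.3.1 with an overlap rule: a medication counts in every period in which it was taken. It counts in the OLE if it started after the first OLE dose, or started earlier and continued into the OLE. For a start on the day of the first OLE dose, use the TEAE rule in SAP 4.7.1: compare times where they exist, and otherwise assign the start to the OLE. State that SAP 4.3.2 follows the same rule for procedures.

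The cost is one sentence and a change to the derivation, which would use stop dates or ongoing status as well as start dates. The downside is that a medication can appear in both period tables, so the two columns cannot be added. A footnote should say so.
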